3. DESCRIPTION OF STUDY DESIGN

This study will be a multicenter, randomized, double-blind, placebo-controlled, parallel group study of three different strengths of SM04690 injected into the target knee joint of moderately to severely symptomatic osteoarthritis subjects.

Approximately 445 subjects will be enrolled and randomized at a ratio of 1:1:1:1 (0.03 mg active per 2 mL injection: 0.07 mg active per 2 mL injection: 0.23 mg active per 2 mL injection: placebo). Subjects will participate in a screening period of up to 21 days and a 52 week follow-up period. Clinic visits will be scheduled at Screening, Treatment Visit Day 1 and Follow-up Weeks 4, 13, 26, 39 and 52 [End of study (EOS) or Early Termination (ET)].

The study schedule is as follows:

- Day -21 to -1: Screening Visit
- Day 1: Treatment visit
- Week 4: Follow-up visit
- Week 13: Follow-up visit
- Week 26: Follow-up visit

- Week 39: Follow-up visit
- Week 52: End of Study (EOS) or Early Termination (ET): Follow-up visit

Specific timing of protocol procedures are described in [Appendix 1](#).

This study will be conducted at up to 40 investigational centers in the US. Potential subjects will attend a Screening Visit and participate in a screening period of no longer than 21 days.

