5.6. X-Ray of Knee Joints

X-ray of the knee joints will be taken during the screening period and follow-up visit Weeks 26 and 52 (EOS)/Early Termination. The screening X-ray is to be taken within 21 days before study visit Day 1 and must be taken according to the guidance provided by the independent radiologist.

Detailed instructions for obtaining and managing the X-rays will be provided to the

investigational center prior to the initiation of subject enrollment. The intent (and included in the Image Review Charter – Image Acquisition guidelines) is that X-rays should be obtained in the posterior-anterior (PA) view, whenever possible. The Image Acquisition Protocol allows for anteroposterior (AP) view when PA view X-ray cannot be acquired.

All radiographs will be submitted to an independent radiologist who will document disease stage according to the Kellgren-Lawrence grading scale for compliance with enrollment criteria, as well as joint space width for efficacy assessments.

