10.2. Randomization

Subjects will be randomized 1:1:1:1 (0.03 mg active per 2 mL injection: 0.07 mg active per 2 mL injection: 0.23 mg active per 2 mL injection: placebo) to each dose group using a permuted block design stratified by each site. Specific information regarding the use of Medidata Balance to store and implement the permuted block design will be detailed within the statistical analysis plan.

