2.1. Sample Size

A sample size of approximately 445 subjects will be randomized at a ratio of 1:1:1:1 (0.03 mg active per 2 mL injection : 0.07 mg active per 2 mL injection : 0.23 mg active per 2 mL injection : placebo). The sample size for this study was based upon accepted statistical practice to establish an acceptable level of precision with respect to treatment effect estimation ([Piantadosi 1997](#)).

To explore possible power expected from this study design, an analysis of covariance regression model was simulated via a Monte Carlo simulation of 1000 replicates. The simulation model estimated a change in WOMAC Pain from baseline comparison between SM04690 and placebo adjusting for baseline WOMAC Pain. The following assumptions were made for the power simulation:

- Sample size of 100 subjects per group,
- Type 1 error rate of 5%,
- WOMAC Pain Baseline average is 11 points [scale 0-20] with a standard deviation of 3,
- WOMAC Pain Baseline is the same for both treatment and placebo groups,
- Treatment change from baseline is -5.8 points, leading to a final score of 5.2 points [scale 0-20]
- Historical placebo change from baseline is -3.5 points, leading to a final score of 7.5 points [scale 0-20]
- Final pain score has standard deviation of 4 and is the same for both treatment and placebo groups, and
- Correlation between baseline and final pain score is 0.1.

The WOMAC Pain subscore parameters were based upon observed data from the 0.07 mg group in SM04690-01. Based upon these assumptions, SM04690-OA-02 is estimated to have 95.8% power.

A simulation model for WOMAC Function was also estimated. The following assumptions were made for the power simulation:

- Sample size of 100 subjects per group,
- Type 1 error rate of 5%,
- WOMAC Function Baseline average is 39 points [scale 0-68] with a standard deviation of 11,
- WOMAC Function Baseline is the same for both treatment and placebo groups,
- Treatment change from baseline is -19.5 points, leading to a final score of 19.5 points [scale 0-68]
- Historical placebo change from baseline is -13.5 points, leading to a final score of 25.5 points [scale 0-68]
- Final function score has standard deviation of 15 and is the same for both treatment and placebo groups, and
- Correlation between baseline and final function score is 0.1.

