2.2. Randomization

Subjects will be randomized 1:1:1:1 (0.03 mg active per 2 mL injection : 0.07 mg active per 2 mL injection : 0.23 mg active per 2 mL injection : placebo) to each dose group using Medidata Balance with a permuted block design stratified by study site. A block size of 8 has been selected for this study.

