5.2. Handling of Missing Data

Multiple imputation will be utilized for the primary and secondary analyses. Missing data will be imputed based upon the observed data for each outcome under the missing at random (MAR) assumption following the paradigm first developed by Rubin (Schafer 1999). The imputation will adjust for the outcome’s baseline data in a regression model with data imputed independently for each timepoint; any missing baseline data will also be imputed. A total of 10 imputation datasets will be created and analyzed based upon accepted convention (Schafer 1999). Error estimates of the multiple imputation itself as well as an overall summary of the efficacy analysis will be averaged across the 10 imputed datasets based upon Rubin’s paradigm.

Specifically, let Q denote the imputed mean of an efficacy outcome Y subject to missing data at a given timepoint, where the estimate of that mean for any i^{th} imputation would be defined as function of both observed and missing data such that

$$\widehat{Q}^{(i)} = E\left(Q^{(i)} | Y_{observed}, Y_{missing}^{(i)}, Y_{Baseline}, I(Group)\right), i = 1, \dots, 10.$$

After all 10 datasets have been imputed, the overall estimate of Q is a simple average defined as

$$\bar{Q} = \frac{\sum_{i=1}^{10} \widehat{Q}^{(i)}}{10}.$$

For this analysis using 10 imputed datasets, the variance of \bar{Q} is defined as

$$Var(\bar{Q}) = 1.1B + \bar{U}$$

where B is the between imputation variance and U is the within imputation variance:

$$B = \frac{1}{9} \sum_{i=1}^{10} (\widehat{Q}^{(i)} - \bar{Q})^2;$$

$$\bar{U} = \frac{\sum_{i=1}^{10} U^{(i)}}{10}.$$

Imputations will be performed with a seed of 201610141.

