8.1.1. ANCOVA Model for Continuous Efficacy Outcomes

ANCOVA models will be used for all continuous efficacy outcome measures summarized by change from baseline in order to test the following three hypotheses:

$$H_0: (\beta_i - \beta_0) = 0$$

$$H_A: (\beta_i - \beta_0) \neq 0, \text{ where } i = 1,2,3$$

In the statement above, β is the least squares estimate in the change in the continuous efficacy outcome from baseline at each timepoint (where β_0 is the estimate for placebo), and i represents each of the three SM04690 treatment groups.

Least squares estimate of difference between each treatment group and placebo in the change in the continuous efficacy outcome from baseline at each timepoint, adjusted for baseline value, will be reported along with unadjusted 95% confidence intervals and P values.

Continuous efficacy measures to be analyzed by the ANCOVA model include:

- WOMAC Pain
- WOMAC Function
- WOMAC Total
- Patient Global Assessment
- Physician Global Assessment
- Medial and Lateral Joint Space Width
- SF-36

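### Randomisation is stratified by site, but the ANCOVA and the imputation model leave site out without a reason; if sites differ, the tests are slightly conservative, and a random site intercept corrects this at little cost

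*SAP*

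**What the plan says.** Both documents stratify the randomisation by site. Protocol 10.2 specifies a "permuted block design stratified by each site". SAP 2.2 does the same, "with a permuted block design stratified by study site. A block size of 8 has been selected for this study". Protocol section 3 adds: "This study will be conducted at up to 40 investigational centers in the US". With about 445 subjects, that is about 11 per site (445/40).

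The analysis does not use site:

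- **ANCOVA (SAP 8.1.1).** Differences from placebo are "adjusted for baseline value, will be reported along with unadjusted 95% confidence intervals and P values". Baseline is the only adjustment named. The SAP prints no full model equation, so the absence of site is read from this sentence.
- **Imputation (SAP 5.2).** The model uses the outcome's "baseline data in a regression model with data imputed independently for each timepoint". The displayed conditional expectation contains baseline and group, and no site term.
- **Power (SAP 2.1).** The simulation was a "comparison between SM04690 and placebo adjusting for baseline WOMAC Pain".

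Protocol 10.5.5 says only that parametric ANCOVA will be used. Site is not among the subgroup covariates in SAP 8.2.2. Neither document gives a reason for omitting site, plans a sensitivity analysis with it, or states a between-site variance.

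**The concern.** An analysis should normally reflect the factors on which randomisation was restricted. Blocking within site makes the arms roughly balanced at each site, so differences between sites partly cancel in the treatment contrast. A model without site does not recognise this. It counts the between-site variance as residual noise and reports a standard error larger than the true one. The cost is power, not validity.

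Power matters most at WOMAC Function. SAP 8.2.1 tests 21 hypotheses in a strict order at 0.05, and the first failure makes all later tests exploratory. H4 (Function at Week 13, 0.07 mg) comes before H5 to H21, which is 17 tests. Function also has the lower stated power, 78.5% against 95.8% for Pain.

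For joint space width, differences between site readers are not part of this argument, because "All radiographs will be submitted to an independent radiologist". The binary responder endpoints are exploratory, lie outside the hierarchy and are not covered here.

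**Working it through.** **Inputs from SAP 2.1.** 100 per group; 5% type I error (two-sided, from the alternative in SAP 8.1.1); baseline-to-final correlation 0.1. Function: difference 19.5 − 13.5 = 6, final SD 15. Pain: difference 5.8 − 3.5 = 2.3, final SD 4.

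**Assumption.** Site ICC (site share of residual variance, total variance held fixed) of 0, 0.02, 0.05 or 0.10. The documents give no value.

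**The SAP's own power.** SE = SD × √(1 − 0.1²) × √(2/100); power = Φ(difference/SE − 1.96).

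- Function: SE = 15 × 0.995 × 0.1414 = 2.111; Φ(2.843 − 1.96) = 81.1% (stated 78.5%).
- Pain: SE = 4 × 0.995 × 0.1414 = 0.563; Φ(4.086 − 1.96) = 98.3% (stated 95.8%).

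Both are about 2.5 points above the stated figures. That is a separate matter and does not affect a comparison of models with and without site.

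**Upper bound: complete balance within every site.** The true SE is then SE × √(1 − ICC), while the baseline-only model still reports SE.

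- SE overstatement = 1/√(1 − ICC) − 1
- Baseline-only type I error = 2 × [1 − Φ(1.96/√(1 − ICC))]
- Baseline-only power = Φ((difference/SE − 1.96)/√(1 − ICC))
- Power with site = Φ(difference/(SE × √(1 − ICC)) − 1.96)

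| ICC | SE overstated | Type I, no site | Function power, no site → site (100 per arm) |
|---|---|---|---|
| 0 | 0% | 5.0% | 81.1 → 81.1% |
| 0.02 | 1.0% | 4.8% | 81.4 → 81.9% |
| 0.05 | 2.6% | 4.4% | 81.7 → 83.1% |
| 0.10 | 5.4% | 3.9% | 82.4 → 85.0% |

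**Realistic case: incomplete blocks.** At about 11 subjects per site with blocks of 8, many sites end on an unfilled block. Simulation: four arms, 40 sites of unequal size, blocks of 8 filled within site, N = 400, 32,004 replicates per ICC, one dose against placebo in a model with all four arms. The random intercept was fitted by REML with df = N − sites − 4.

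| | ICC 0 | 0.02 | 0.05 | 0.10 |
|---|---|---|---|---|
| Function power, baseline only | 80.1% | 80.8% | 81.3% | 82.0% |
| Function power, random site intercept | 80.3% | 81.3% | 82.4% | 84.4% |
| Paired gain, points (Monte Carlo SE) | 0.14 (0.03) | 0.50 (0.04) | 1.07 (0.06) | 2.43 (0.09) |
| Function power, fixed site effects | 79.0% | 80.3% | 81.4% | 83.6% |
| Type I, baseline only | 5.1% | 4.9% | 4.6% | 4.2% |
| SE overstated, baseline only | about 0% | 0.5% | 2.0% | 4.3% |
| Pain gain, points (from about 98%) | 0.0 | 0.1 | 0.2 | 0.4 |

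Type I error with the random intercept was 5.0 to 5.1% throughout. The simulated power levels lie up to about one point below the closed form (80.1% against 81.1% at ICC 0). The gain is paired within each simulated dataset, so it does not depend on that level.

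**At the planned size, N = 445** (12,004 replicates), the Function gain is 0.1, 0.4, 1.1 and 2.0 points. A separately coded simulation (6,000 replicates, uneven sites) gave Function power of 84.9 → 85.1%, 85.3 → 85.7%, 84.2 → 85.2% and 85.9 → 88.4%. At ICC 0.10 its baseline-only model reported a mean SE of 2.00 against a true 1.905. The random intercept reported 1.908 against 1.894.

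**The case against.** The strongest reply is that nothing here is invalid. A pre-specified, slightly conservative ANCOVA is acceptable, all the more in a study that Protocol 10.1 calls exploratory. The following points stand:

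- **The estimate itself is hardly sharper.** Blocking has already delivered the precision. In the N = 445 run at ICC 0.10 the true SE was 1.905 without site and 1.894 with it. The gain comes from reporting a correctly sized SE and so using the full 5%.
- **Some of the gain is not real recovery.** About 0.15 point appears even at ICC 0, where ordinary ANCOVA is exact. That is a noticeable share of the 0.5 point at ICC 0.02.
- **The inputs cover one dose.** SAP 2.1 takes its effects from the 0.07 mg group, so the figures describe H1 and H4. For 0.03 mg and 0.23 mg they hold only if the effect is the same. Patient Global Assessment and joint space width are not quantified.
- **Imputation was not simulated.** The planned imputation agrees with the planned ANCOVA, so it is not a separate defect. Site is needed there only once it enters the analysis model.
- **Function is reached only if H1 to H3 all succeed.**

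These points limit the size of the issue. They do not explain why site was left out, and they do not show a material cost of including it.

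**Conclusion.** The concern holds as a minor point of efficiency and of matching the analysis to the design. The plan stratifies by site, analyses and imputes without it, and gives no reason. If sites differ, the baseline-only standard errors are too large: by about 2% at ICC 0.05 and 4% at ICC 0.10. For Function at the 0.07 mg effect, a random site intercept is worth about half a point of power at ICC 0.02, one point at 0.05 and 2 to 2.5 points at 0.10. For Pain it is negligible.

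There is no bias and no inflation of type I error. The omission does not overstate the SAP's power either, because that was simulated with the same baseline-only model. The result rests on an assumed ICC of 0 to 0.10, 40 sites of unequal size and no missing data.

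**What to change.** Before the Week 26 unblinding, amend the SAP as follows:

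1. Add a random site intercept to the ANCOVA for all continuous endpoints and name the degrees-of-freedom method.
2. State that a site variance estimated at zero leaves the planned ANCOVA.
3. Include site in the imputation model and say in what form, so that imputation and analysis agree.
4. Do not use unpooled fixed effects for up to 40 sites. They lose about 1 point of Function power at ICC 0 and only break even near 0.05.
5. If site is still left out, give the reason.

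Timing matters because the sponsor is unblinded at Week 26 (Protocol 3.2.4) and SAP 8.3 does not allow the interim efficacy analyses to be rerun. A site term added later could look data-driven.

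No new data are needed, since site is known for every subject. The costs are a mixed model in place of ordinary ANCOVA and some added specification for imputation with site. The likelihood ratio test for subgroup interactions in SAP 8.2.2 must then compare maximum likelihood fits, not REML fits.

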8.1.2. Logistic Regression Model for Binary Efficacy Outcomes

Logistic regression will be used to analyze the proportion of positive responses within each treatment group compared to placebo at each timepoint for all binary efficacy outcomes. Odds ratios as well as unadjusted 95% confidence intervals and P values will be presented.

Binary efficacy measures to be analyzed by logistic regression include:

- OMERACT-OARSI “strict” response
- OMERACT-OARSI response

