
Statistical methods: A sample size of approximately 445 subjects will be randomized across four treatment groups (0.03 mg active per 2 mL injection: 0.07 mg active per 2 mL injection: 0.23 mg active per 2 mL injection: placebo) based on a 1:1:1:1 ratio. The sample size for this study was based upon accepted statistical practice and not on a formal efficacy hypothesis test and corresponding power analysis.
 
The Safety Analysis Set will comprise all subjects who were randomized and received SM04690 or placebo. The Intent-to-Treat Analysis Set (ITT) will comprise subjects who were randomized. The Modified Intent-to-Treat Analysis Set (mITT) will comprise all randomized subjects who received a protocol specified dose of SM04690 or placebo. The Per Protocol Analysis Set (PP) will comprise ITT subjects who complied with all study procedures and evaluations, and did not have major protocol deviations.
 
The incidence of AEs and proportion of subjects experiencing AEs will be summarized by

seriousness and relatedness to study product for each treatment group; severity of the AEs will be assessed by the Investigator according to the “Guidance for Industry: Toxicity Scale for Healthy Adult and Adolescent Volunteers Enrolled in Preventive Vaccine Trials”. Safety summaries will also include listings of clinical laboratory findings, vital signs, and concomitant medications.

Differences in efficacy outcomes between groups will be estimated at time points using parametric regression methods adjusting for baseline.

TABLE OF CONTENTS

SPONSOR SIGNATURE PAGE	2
PRINCIPAL INVESTIGATOR’S SIGNATURE PAGE.....	3
SYNOPSIS	4
TABLE OF CONTENTS.....	10
LIST OF TABLES.....	13
LIST OF ABBREVIATIONS AND DEFINITIONS OF TERMS.....	14
1. INTRODUCTION	16
1.1. Summary.....	16
1.2. Nonclinical Assessments	16
1.3. Study Rationale.....	16
2. STUDY OBJECTIVES AND PURPOSE	17
2.1. Purpose	17
2.2. Study Objectives.....	17
3. DESCRIPTION OF STUDY DESIGN	18
3.1. Study Endpoints.....	19
3.1.1. Primary Endpoints	19
3.1.2. Secondary Endpoints	19
3.1.3. Exploratory Endpoints.....	19
3.2. Measures to Minimize Bias	20
3.2.1. Blinding	20
3.2.2. Randomization/Assignment to Investigational Product or Placebo	20
3.2.3. Subject Re-screening.....	20
3.2.4. Unblinding During the Study.....	20
3.3. Investigational Product	21
3.3.1. Rationale for Dosages and Dosing Regimen	21
3.3.2. Dosages and Dosing Regimen	22
3.3.3. Dose Modifications.....	22

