10.5.5. Efficacy Analysis

Efficacy analysis will be performed on the ITT, mITT, and PP Analysis Sets. Change in primary and secondary efficacy endpoints from baseline will be estimated at specified time points using parametric analysis of covariance (ANCOVA) models. Formal hypothesis testing between treatment groups will be conducted using a strategy to control the familywise error rate; the error rate strategy is detailed in the study's SAP.

Exploratory efficacy analysis will be performed on the ITT, mITT, and PP analysis sets. Change in WOMAC total, WOMAC pain subscore, WOMAC function subscore, Patient Global Assessment, Physician Global Assessment, JSW and HRQOL from baseline will be estimated at specified time points using parametric analysis of covariance (ANCOVA) models. Logistic regression will be used to analyze the proportion of OARSI responders within each treatment group compared to placebo at specified time points. Exploratory subgroup analyses may also be performed.

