1.3. Exploratory Objectives

Additional exploratory objectives of this study include:

- Evaluate change from baseline in WOMAC total score for the target knee at Weeks 4, 13, 26, 39 and 52
- Evaluate change from baseline OA pain in the target knee as assessed by the WOMAC pain subscore at Weeks 4, 39 and 52
- Evaluate change from baseline OA function in the target knee as assessed by the WOMAC function subscore at Weeks 4, 39 and 52
- Evaluate change from baseline OA disease activity as assessed by the Patient Global Assessment at Weeks 4, 39 and 52
- Evaluate change from baseline in medial JSW as documented by X-ray of the target knee at Week 52
- Evaluate change from baseline in lateral JSW as documented by X-ray of the target knee at Weeks 26 and 52

- Determine the percentage of Outcome Measures in Rheumatology Clinical Trials (OMERACT)-Osteoarthritis Research Society International (OARSI) responders and “strict” responders at Weeks 4, 13, 26, 39 and 52
- Evaluate change from baseline health-related quality of life (HRQOL) as assessed by the 36-Item Short Form Health Survey (SF-36) at Weeks 4, 13, 26, 39 and 52
- Evaluate change from baseline OA disease activity as assessed by the Physician Global Assessment at Weeks 4, 13, 26, 39 and 52

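### The responder logistic regression in SAP 8.1.2 names no baseline covariate, although the protocol synopsis promises baseline adjustment; responder missing-data handling is also left open

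*SAP*

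**What the plan says.** - **Protocol synopsis, Statistical methods:** "Differences in efficacy outcomes between groups will be estimated at time points using parametric regression methods adjusting for baseline". No outcome is excepted, and the synopsis lists OMERACT-OARSI responders among its efficacy criteria.
- **Protocol 10.5.5:** "Logistic regression will be used to analyze the proportion of OARSI responders within each treatment group compared to placebo at specified time points". No covariate is named.
- **SAP 8.1.1 (continuous outcomes):** treatment differences are "adjusted for baseline value, will be reported along with unadjusted 95% confidence intervals and P values".
- **SAP 8.1.2 (binary outcomes):** "Logistic regression will be used to analyze the proportion of positive responses within each treatment group compared to placebo at each timepoint", followed by "Odds ratios as well as unadjusted 95% confidence intervals and P values will be presented". No covariate is named.
- **SAP 5.2:** "Multiple imputation will be utilized for the primary and secondary analyses". Each outcome is imputed from its own baseline, separately at each timepoint.
- **SAP 5.4:** early-termination assessments outside a visit window count as missing and are handled under 5.2. No endpoint tier is mentioned.
- **SAP 1.3:** the responder objective is in the list opened by "Additional exploratory objectives of this study include".
- **SAP 8:** all efficacy analyses use the ITT set.

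**The concern.** Response is defined by percentage and absolute improvement from baseline, so its probability can depend on where a subject starts. Baseline pain, function and Patient Global are collected on everyone. A programmer following 8.1.2 literally would fit treatment alone, which departs from the synopsis and leaves some precision unused.

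The same programmer would find no rule for a subject whose responder status is missing. At Weeks 13 and 26, pain, function and Patient Global are imputed as primary or secondary outcomes. One report could therefore show imputed component results for all randomized subjects beside responder rates for a smaller subset that nobody defined in advance.

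**Working it through.** **1. What unadjusted means.** The word describes the intervals and P values in both 8.1.1 and 8.1.2. In 8.1.1 the model is baseline-adjusted, so the word most naturally refers to multiplicity. It does not show that 8.1.2 intends a model without covariates. The case rests on 8.1.1 naming the covariate and its parallel section not doing so.

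**2. The plan's own figures.** The SAP gives no power or expected rate for responders. Its power figures concern the continuous ANCOVA. Power = Φ(δ/(SD√(1−r²)·√(2/n)) − 1.96), with n = 100 and r = 0.1:
- Pain: δ = 2.3, residual SD 3.98, so Φ(4.09 − 1.96) = 98.3% (SAP: 95.8%).
- Function: δ = 6.0, residual SD 14.925, so Φ(2.84 − 1.96) = 81.1% (SAP: 78.5%).

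This mismatch does not bear on the present point. Only the SAP's inputs are used below.

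**3. Pain-only strict response.** SAP 2.1 inputs multiplied by 5 to a 0–100 scale: baseline 55 (SD 15), final mean 26 on active and 37.5 on placebo (SD 20). Strict response is at least 50% and at least 20 points. A simulated population of 200,000 per arm, with z scaled to 111 per arm (445/4 = 111.25), gives:

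| r | Response rates | OR without baseline | OR with baseline | z without | z with |
|---|---|---|---|---|---|
| 0.1 (SAP) | 51.8% vs 30.9% | 2.41 | 2.55 | 3.14 | 3.23 |
| 0.5 (assumed) | 51.8% vs 27.1% | 2.89 | 2.90 | 3.72 | 3.72 |

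At r = 0.1, power goes from Φ(3.14 − 1.96) = 88.1% to Φ(3.23 − 1.96) = 89.8%, a gain of 1.7 points.

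The gain vanishes for a simple reason. The 50% rule raises the allowed final score by 0.5 per baseline point, while the expected final score rises by r × 20/15. That is 0.13 at r = 0.1, so baseline predicts response. It is 0.67 at r = 0.5, close enough to 0.5 that baseline predicts little.

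**4. Composite response.** This uses the SAP's pain and function effects, 111 per arm and r = 0.1. Patient Global values and between-component correlations are assumed, because the documents give neither.
- Strict: 83.9% to 85.1% (+1.2).
- Full response: 70.4% to 75.7% (+5.3).
- At r = 0.5: no gain.

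**5. Missing data: why the rule matters.** The documents give no dropout or responder rates. Assume 55% vs 35% response among those observed, a complete-case difference of 20 points. Counting missing as non-response gives 0.55(1 − m₁) − 0.35(1 − m₀), where m₁ and m₀ are the missing fractions on active and placebo:

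| Missing, active / placebo | Difference |
|---|---|
| 5% / 5% | 52.25 − 33.25 = 19.0 |
| 10% / 10% | 49.5 − 31.5 = 18.0 |
| 20% / 20% | 44.0 − 28.0 = 16.0 |
| 5% / 15% | 52.25 − 29.75 = 22.5 |
| 15% / 5% | 46.75 − 33.25 = 13.5 |

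Extreme bounds at 20% missing in both arms run from 44 − (28 + 20) = −4 to (44 + 20) − 28 = +36 points.

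**6. Why the imputations in 5.2 cannot simply be reused.** They draw each component separately, which breaks the correlation between components. A rule of the form *one of two, or two of three* is then met too often. With assumed component correlations of 0.6 to 0.8 and assumed Patient Global values, response among fully imputed subjects rises from about 61–66% to 73–76%, and strict response from 38–46% to 49–54%.

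**The case against.** The synopsis sentence is general. Protocol 10.5.5 is the operative section, and it matches SAP 8.1.2. Protocol 10 defers full detail to the SAP. Response is already measured against baseline, and the endpoint is exploratory. It is fair to call the omission silence rather than a declared unadjusted model, and the low stakes stand. But the synopsis makes no exception for responders, and the covariates cost almost nothing.

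A reader might go further and infer that responder rates will come from complete cases only. The documents do not say so. SAP 5.4 sends some missing visits to 5.2 whatever the endpoint, SAP 8 requires the ITT set, and the components are imputed at Weeks 13 and 26. Complete case is what logistic software does by default, and 5.4 does not reach a skipped item or a missed visit in a subject who stays in the study. It is therefore likely, but unstated.

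A reader might also infer that any missing component removes the subject. SAP 3.2.2 does not support that. Strict response ignores Patient Global, and pain or function alone can satisfy it. If pain and function are observed, a missing Patient Global matters only when condition A fails and exactly one of the two meets the lower threshold. The rule in SAP 3.2.1 that one missing item voids a domain score therefore does not translate directly into lost responders.

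**Conclusion.** The point holds as a minor improvement. SAP 8.1.2 should carry the baseline adjustment that the synopsis promises and 8.1.1 applies. The gain is about 1 to 5 power points at the SAP's correlation of 0.1 and none at 0.5; the composite figures also depend on assumed Patient Global values and component correlations.

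The missing-data question is a real gap in specification, because 5.2 and 5.4 point in different directions for an exploratory endpoint. In the assumed example the choice between complete cases and non-response moves the difference from 20 points to between 13.5 and 22.5. H1 to H21 are unaffected, and the plan states that no adaptation follows from the interim.

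**What to change.** 1. In SAP 8.1.2, add baseline WOMAC pain and function as covariates for both responder endpoints, plus baseline Patient Global for the full response.
2. Report a standardised risk difference beside the odds ratio, which becomes conditional on baseline.
3. Reconcile SAP 5.2 with 5.4, and state the responder missing-data rule for every visit at which SAP 1.3 lists responders.
4. If response is derived from imputed data, impute pain, function and Patient Global jointly at each visit instead of separately. Classify directly any subject whose status is already settled by observed components, derive the rest within each imputed data set, and pool by Rubin's rules.

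The cost is SAP wording, some programming and, under item 4, one joint imputation model. The changes should be in place before the sponsor is unblinded for the Week 26 interim, which includes responder analyses.
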